6.2 Study Visits and Procedures

There is only one study visit.

7. TRIAL MATERIALS

AIR+ KN95 Mask tested according to the KN95 protocol for respirators

- AE220L
- AE220M
- AE220S

8. TREATMENT

Not applicable

9. SAFETY MEASUREMENTS

9.1. Definitions

No adverse events are anticipated.

9.2. Collecting, Recording and Reporting of "Unanticipated Problems Involving Risk to Subjects or Others" - UPIRTSO events to the NHG Domain Specific Review Boards (DSRB)

NAD

9.3. Collecting, Recording and Reporting of Serious Adverse Events (SAEs) to the Health Science Authority (HSA)

No drugs are used.

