2.3. Secondary Objectives

The secondary outcomes include other physiological parameters such as oxygen saturation (SPO2), heart rate (HR) and respiratory rate (RR). In addition, we will assess the general well-being and comfort level of the child when wearing the AIR+ KN95 Mask.

2.4. Potential Risks and benefits:

a. End Points - Efficacy

There is no direct benefit in participating in this research. However, the knowledge gained would benefit other children and the public in the future. The results from this research will enable us to test the safety of the use of Air+ KN95 masks in children. This study will measure the carbon dioxide levels inside the mask and in the children as they wear it.

b. End Points - Safety

The study is designed to observe the impact of wearing the Air+ KN95 mask in children while at rest and on minimal exertion only. They may experience mild discomfort when wearing the mask whilst brisk walking on the treadmill. However, their vital signs will be monitored, and they will be encouraged to remove the mask if they feel uncomfortable.

Studies have shown that prolonged wearing of disposable particulate respirators may lead to an increase in carbon dioxide (CO2) levels which may result in headaches, increased irritability, or breathing discomfort. Usually, this is resolved by simply removing the mask.

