3.5. Withdrawal Criteria

Subjects may withdraw voluntarily from participation in the study at any time.

Also, subject will be withdrawn from the study if there is clinical suspicion of hypercarbia or the physiological parameters exceed their threshold:

- ETCO₂ > 50mmHg for at least 3 minutes sustained
- SPO₂ < 92%
- HR and RR within 2.5 and 97.5 centiles by age as proposed by Wallis LA *et al*:

- Subject complains of symptoms such as dizziness & confusion, even if ETCO₂ or SPO₂ levels remain within the specified normal range i.e., ETCO₂ \leq 50mmHg and SPO₂ \geq 92%

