5. STUDY DESIGN

5.1. Summary of Study Design

This study is designed to explore and determine whether the new disposable particulate respirator is safe and effective for use in healthy children aged 7 to 14 years of age.

Figure 1 shows the algorithm of the summary design.

[figure not shown]

Figure 1. Study Design

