9.4. Safety Monitoring Plan

Data will be coded at source and identifiers will also be removed

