11.2. Statistical and Analytical Plans

a. General Considerations

The primary outcome of the study is ETCO₂. The 95% upper confidence limit of the increase in ETCO₂ after wearing a mask will be computed. The proportion and its associated 95% confidence intervals of children whose ETCO₂ are > 50mmHg for at least 3 minutes sustained will also be presented. Similar analysis will be carried out for other physiological parameters such as SPO₂, HR and RR. In addition, the change in mean of visual analogue scale after the child wears the mask will be compared using the paired-t test and adjusted for baseline imbalance using regression analysis.

These analyses will be repeated for physiological parameters collected while at rest and on mild exertion.

b. Safety Analyses

NAD

c. Interim Analyses

This will not be done.

d. Describe the types of statistical interim analyses and stopping guidelines (if any) that are proposed, including their timing.

NAD

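### The study is meant to establish that the mask is safe in children, but plans no adverse-event collection and no analysis of symptoms, mask removals or withdrawals by reason

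*Combined protocol and SAP*

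**What the plan says.** **Purpose.** Section 5.1: "This study is designed to explore and determine whether the new disposable particulate respirator is safe and effective for use in healthy children". Section 2.4 a: "The results from this research will enable us to test the safety of the use of Air+ KN95 masks in children".

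**Where event data would be planned.**
- 9.1 (Definitions): "No adverse events are anticipated".
- 9.2 (reporting of unanticipated problems to a review board): NAD.
- 9.3 (serious adverse event reporting to the regulator): "No drugs are used".
- 9.4 (Safety Monitoring Plan): "Data will be coded at source and identifiers will also be removed".
- 11.2, under "b. Safety Analyses": NAD. The abbreviation is not explained.

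**Symptoms that the protocol itself mentions.** Section 1.1 links raised CO2 from prolonged respirator wear to headache, irritability and difficulty breathing. Section 2.4 b repeats the link ("which may result in headaches, increased irritability, or breathing discomfort") and adds that mild discomfort may occur on the treadmill, in which case children are encouraged to take the mask off. Section 3.5 includes among the reasons for withdrawal "Subject complains of symptoms such as dizziness & confusion", and says that this applies even when ETCO2 and SPO2 are in the normal range.

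**What is analysed (11.2 a).** The 95% upper confidence limit of the ETCO2 increase; the proportion of children with sustained ETCO2 above 50 mmHg, with a 95% confidence interval; similar analyses of SPO2, HR and RR; and the change in mean on a visual analogue scale. All are repeated at rest and on mild exertion.

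**Drop-outs.** Section 3.6 replaces them.

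**The concern.** A safety conclusion about a device worn on the face rests partly on how the wearer felt and whether the device had to come off. The protocol names these effects and acts on them during the test, but has no plan to carry them into the results.

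The measures that are analysed cannot stand in for symptoms, because Section 3.5 accepts that a child may have symptoms with normal ETCO2 and SPO2. A report that followed the plan could call the mask safe on physiology and a mean comfort score. It need not say how many children had headache, felt dizzy, took the mask off or were withdrawn for symptoms.

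**Working it through.** The plan gives no figure for symptoms, so the main check is a reading of the sections against one another. A short calculation then shows what the missing data could tell us.

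**Step 1. Is symptom collection planned anywhere else?**
- Section 4 and Section 6.1 b record biometric data, fit, physiological parameters and the visual analogue scale. No symptom item appears.
- Section 6.1 e (discontinuation procedures) says only that subjects may withdraw. It does not ask for a reason.
- Section 11.2 a lists no symptom, mask-removal or withdrawal outcome.

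**Step 2. Could the analysed outcomes capture these events indirectly?**
- The proportion with sustained ETCO2 above 50 mmHg matches the first withdrawal criterion in 3.5, so those withdrawals have a counterpart in the analysis.
- Withdrawal for symptoms with normal ETCO2 and SPO2 has no counterpart.
- The visual analogue scale is a global rating, taken at the end of the procedure and summarised as a mean. It itemises no symptom, and a child withdrawn early may never complete it.

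**Step 3. Are withdrawn children kept in view?** Section 11.1 requires at least 80 children and recruits 100 to allow for withdrawals, so the plan makes room for 100 − 80 = 20. Section 3.6 also replaces drop-outs. Neither section says whether a withdrawal under 3.5 counts as a drop-out, or whether data up to withdrawal are analysed.

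**Step 4. Would counts be informative at this size?** Inputs: n = 80 and n = 100 from 11.1. The event counts and true rates are assumptions for illustration.

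Exact two-sided 95% upper limit with no events, 1 − 0.025^(1/n):
- n = 80: 1 − 0.025^(1/80) = 4.5%
- n = 100: 1 − 0.025^(1/100) = 3.6%

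With 5 events in 100, the Clopper-Pearson 95% limits are 1.6% to 11.3%.

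Chance of at least one event, 1 − (1 − p)^n:

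| Assumed true rate p | n = 80 | n = 100 |
|---|---|---|
| 1% | 55% | 63% |
| 2% | 80% | 87% |
| 5% | 98% | 99% |

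A study of this size would therefore probably see a symptom that affects 2% or more of children, and could bound its rate usefully. Without collection it can state no rate or bound.

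**The case against.** The strongest reply is that this is already a safety study. ETCO2, the proportion above 50 mmHg, SPO2, HR and RR are its safety outcomes, and 11.1 calls 50 mmHg a safety threshold. That stands: a reader who inferred from the NAD in 11.2 b that no safety analysis exists would be wrong. What is missing is the analysis of symptoms, mask removals and reasons for withdrawal.

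Other points on that side also stand in part:
- **NAD is undefined.** Under Interim Analyses the protocol says in words that none will be done, while NAD fills the template heading after it. NAD cannot be read as a deliberate decision to analyse nothing. The headings of 9.2 and 9.3 concern reporting to outside bodies and do not by themselves settle what is recorded. On any reading, though, no plan is given.
- **9.1 is not flatly contradicted by 1.1 and 2.4 b.** They speak of what prolonged wear may do. Section 1.1 reports no significant CO2 retention with the predecessor mask, and the session lasts about 50 minutes. The tension is closest with the mild discomfort mentioned in 2.4 b and the symptom withdrawals in 3.5.
- **Dizziness and confusion** are withdrawal triggers in 3.5. The documents do not call them effects of the mask.
- **The case report form and Figure 1 are not visible.** Symptoms may be noted in practice. The text still does not require it and plans no analysis of them.

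**Conclusion.** The gap is real and should be closed, but it is narrower than an absence of safety analysis. The protocol aims to determine safety, defines no adverse events, and plans no collection or tabulation of the symptoms that it names, of mask removals, or of withdrawals by reason. Physiological safety and global comfort are covered.

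A reader might also infer that children withdrawn for safety will be replaced and their data discarded. Section 3.6 does not say so; it leaves both questions open, and affected children may therefore be missing from the results.

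No planned estimate changes in size. What is lost is the ability to state any symptom rate, where no events in 80 or 100 children would have bounded it at 4.5% or 3.6%. Those counts are illustrative. The conclusion assumes that the case report form, which is not shown, adds no symptom items.

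**What to change.** 1. **Section 9.1.** Replace the sentence with a list of the symptoms that the protocol already names: headache, irritability, breathing difficulty or discomfort, dizziness and confusion.
2. **Case report form.** After each test condition actually performed, record yes or no for each symptom. The conditions are taken here to be rest and exertion, each without and with the mask (Sections 1.2 d and 11.2 a); the form should follow the sequence in Figure 1. Also record mask removal in the masked conditions, and the reason for every withdrawal.
3. **Section 11.2 b.** Replace NAD with the number and proportion of children with each event by condition, and withdrawals by reason, with exact 95% confidence intervals.
4. **Denominator.** For each condition, use every child who passed the fit test and started that condition, including those later withdrawn or replaced. List events during the fit test separately. Every child wears a mask at that stage, so counting all who ever put one on would bring in children excluded before any test condition.
5. **Section 3.6.** State whether withdrawals under 3.5 count as drop-outs, and that data up to withdrawal are kept.

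This does not complete the external reporting headings in 9.2 and 9.3, which need separate attention.

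**Cost.** One checklist, one table and a few extra minutes per child, with no added visits or equipment. Self-reports of irritability and confusion will be of limited reliability in the youngest children.

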9.4. Safety Monitoring Plan

Data will be coded at source and identifiers will also be removed

9.5. Complaint Handling -

The PI is responsible for handling complaints and ensuring the safe conduct of the procedures listed above.

10. DATA ANALYSIS

10.1. Data Quality Assurance

Data collection will be performed by the study team members. Training on proper data collection and data entry methods will be provided to all staff involved in the study. A data quality assurance system which will include appointing designated supervisors to oversee the quality of the fieldwork, logic checks on data, etc. will be setup.

10.2. Data Entry and Storage

Data will be collected first in hard copies that will be stored in a locked drawer in the PI's locked office. The data will subsequently be entered into password-protected stand-alone desk top computer in the PI's office as well as a password-protected laptop. All documents will be password protected. Access to the data will be controlled by passwords only known to the investigators and the passwords will be changed periodically.

11. SAMPLE SIZE AND STATISTICAL METHODS

11.1. Determination of Sample Size

It is anticipated that a child at rest will have a mean ETCO₂ of 40 mmHg with standard deviation of approximately 8 mmHg. Based on the proposed safety threshold of 50mmHg and below for the ETCO₂, an increase of 10 mmHg after the subject wears a mask would indicate non-inferiority. A more stringent tolerance level of 5mmHg in ETCO₂ will be assumed given the variability of the ETCO₂ measurements among the children.

Assuming a one-sided test size of 5% and one-sided power of 80%, at least 80 subjects will be required. To account for the children who may withdraw during the study, a total of 100 children will be recruited, distributed across the age groups.

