1.2. Rationale and justification for the Study

a. Rationale for the Study Purpose

Haze is a perennial problem in Singapore. There is a need to consider the development of disposable particulate respirator with enhanced safety and comfort specific for use in children.

ST Engineering Innosparks Pte. Ltd. developed a new type of disposable particulate respirator (AIR+ KN95 Mask) that is suitable for use in both adults and children, from ages 7 and above.

b. Rationale for Doses Selected (not applicable)

No drugs are used in the study.

c. Rationale for Study Population

Commercially available disposable masks designed for occupational use are mainly for adults, such masks do not fit well on children. As the masks under study were developed specifically for school-going children, this study is designed to explore whether the new disposable particulate respirator is safe and effective for use in healthy children aged 7 to 14 years of age.

d. Rationale for Study Design

This study entails the study of subjects doing various activities with and without donning on the mask. The baseline results of subjects without donning on the mask will serve as control.

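### Section 11.1 says a 10 mmHg rise in ETCO₂ would show non-inferiority and then assumes 5 mmHg, while 11.2 ties its upper confidence limit to no margin, so a limit between 5 and 10 mmHg has no fixed reading

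*Combined protocol and SAP*

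**What the plan says.** Section 11.1 assumes a resting mean ETCO₂ of 40 mmHg "with standard deviation of approximately 8 mmHg". From the 50 mmHg safety threshold it then concludes that "an increase of 10 mmHg after the subject wears a mask would indicate non-inferiority". The next sentence reads: "A more stringent tolerance level of 5mmHg in ETCO₂ will be assumed given the variability" among the children. The sample size follows: "Assuming a one-sided test size of 5% and one-sided power of 80%, at least 80 subjects will be required", raised to 100 for withdrawals.

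The comparison is within child. Section 1.2(d) says: "The baseline results of subjects without donning on the mask will serve as control".

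Section 11.2(a) names ETCO₂ as the primary outcome and says: "The 95% upper confidence limit of the increase in ETCO₂ after wearing a mask will be computed". It also presents, with a 95% confidence interval, the proportion of children above 50 mmHg for a sustained 3 minutes or more, and it repeats the analyses at rest and on mild exertion. It gives no margin, no pass/fail rule, no acceptable proportion and no deciding condition. The hypothesis in section 2.1 is an absolute range of 30 to 50 mmHg, which supplies no margin for an increase. No other section sets one.

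**The concern.** A non-inferiority conclusion needs one margin, fixed before the data are seen, and a rule that compares the confidence limit with it. Here the only sentence that mentions non-inferiority carries the figure 10. The figure 5 appears only as a sample-size assumption, and the analysis section uses neither.

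The 10 mmHg sentence is also faulty in itself. It subtracts a group mean (40) from a limit that the plan applies to individual children (50). A mean rise of that size is the point at which the average child reaches the limit. At most it is a boundary to be excluded; observing it would not show that the mask is acceptable.

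At stake is the reading of the primary outcome in a study of healthy children. If the upper limit falls between 5 and 10 mmHg, a report could cite section 11.1 for either conclusion.

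**Working it through.** **Inputs from section 11.1:** resting mean 40, SD 8, threshold 50, candidate margins 5 and 10 (all mmHg), one-sided 5%, power 80%, at least 80 children.

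**Assumed:** the SD of the within-child change, which the plan does not give. If the SD is 8 with and without the mask and the within-child correlation is r, the SD of change is 8 × √(2(1 − r)). This is 8.0 at r = 0.5 and 11.3 at r = 0, and both are carried through. Normal approximation throughout.

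**Step 1. Which margin lies behind the 80?** For paired data with no true difference, n = [SD of change × (1.645 + 0.842) / margin]². For two independent groups the total is four times this with SD 8, rounded up per group.

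| Margin | Paired, SD of change 8 | Paired, SD of change 11.3 | Two groups, total |
|---|---|---|---|
| 5 | 16 | 32 | 64 |
| 10 | 4 | 8 | 16 |

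None gives 80. The nearest variant tried is margin 5, one-sided 2.5%, two independent groups: 82 in total (80.4 unrounded). That matches neither the stated test size nor the paired design. No variant tried with margin 10 exceeds 28, even at one-sided 2.5% and 90% power. The 80 is therefore not reproduced, which is a separate matter, but it points to 5 rather than 10 as the intended margin.

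**Step 2. Width of the upper limit at n = 80.** One-sided 95% upper limit = mean increase + 1.645 × SD / √80.

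- SD 8: 1.645 × 8 / 8.944 = 1.47
- SD 11.3: 1.645 × 11.31 / 8.944 = 2.08

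**Step 3. Where the two margins disagree.** A margin is met when the observed mean increase is below the margin minus that width.

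| SD of change | Meets 5 if mean below | Meets 10 if mean below | Fails 5, passes 10 |
|---|---|---|---|
| 8 | 5 − 1.47 = 3.53 | 10 − 1.47 = 8.53 | about 3.5 to 8.5 |
| 11.3 | 5 − 2.08 = 2.92 | 10 − 2.08 = 7.92 | about 2.9 to 7.9 |

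For example, an observed mean increase of 6 gives an upper limit of 7.5 (8.1 with SD 11.3), which fails at 5 and passes at 10. If the 95% limit in 11.2 means the upper end of a two-sided interval, the widths become 1.75 and 2.48 and the ranges 3.25 to 8.25 and 2.52 to 7.52.

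**Step 4. How often this would matter.** Pass probability = Φ[(margin − true rise) / (SD / √80) − 1.645].

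| True rise | SD of change | Passes 5 | Passes 10 |
|---|---|---|---|
| 0 | 8 | above 99.9% | above 99.9% |
| 0 | 11.3 | 99.0% | above 99.9% |
| 6 | 8 | 0.3% | 99.8% |
| 6 | 11.3 | 0.7% | 94% |
| 10 | either | below 0.1% | 5% |

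The choice of margin makes almost no difference if the mask does not raise ETCO₂. It decides the result if the rise is moderate. The rise of 6 was chosen to lie in the disputed range; it is not a prediction.

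**The case against.** The strongest reply is that there is no real conflict. The two sentences are consecutive, the second calls its figure more stringent, and the natural sense is that 5 replaces 10. Step 1 supports this. That stands, and it means 10 should not be treated as the plan's operative margin. It does not supply the missing rule: the 5 is given as an assumption in the sample-size section, the sentence about 10 remains, and 11.2 refers to neither.

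A reader might infer that the plan would accept a mask that puts half of all children above 50 mmHg. With mean 50 and an unchanged SD of 8, the normal model does put 50% of single values above 50, against 27% at a mean of 45 and 11% at 40. The documents do not support the inference, for two reasons. First, 11.2 plans an upper confidence limit, and under such a rule a true mean rise of 10 meets a 10 mmHg margin only 5% of the time. Second, the plan's individual criterion is more than 50 mmHg sustained for at least 3 minutes, not one value above 50. That the model already places 11% of unmasked children above 50 shows how poorly it stands in for that criterion.

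It can also be said that the study is described as exploratory, that the limit will be reported as a number which readers can judge for themselves, and that individual exceedance is already covered by the planned proportion. The last point is right and should be kept. The first two soften the consequence, but section 11.1 frames the trial in terms of non-inferiority with a test size and power, and a claim in those terms needs its margin stated in the analysis plan.

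**Conclusion.** The concern holds in this form: the plan states one unsound figure for non-inferiority (10), assumes a better one (5), and ties its primary analysis to neither. With 80 children, observed mean increases of about 3.5 to 8.5 mmHg (SD of change 8) or 2.9 to 7.9 mmHg (SD of change 11.3) can be read either way. With no true rise, both margins are met about 99% of the time or more.

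These sizes rest on an assumed SD of change, a one-sided 95% limit and normality. The existence of the gap rests on none of them: any upper limit between 5 and 10 mmHg is affected.

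Two stronger conclusions should not be drawn. The documents do not show that the sponsor means to choose the margin after seeing the data; 5 is the more natural reading. Nor do they show that the planned analysis would pass a mask with a true mean rise of 10 mmHg, except by taking the 10 mmHg sentence literally and ignoring the confidence limit.

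Even with 5 mmHg fixed, a pass would support a statement about the average rise and not, by itself, the section 2.1 hypothesis about the range.

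**What to change.** - **Section 11.1:** reword so that 10 mmHg is described only as the distance from the assumed resting mean to the 50 mmHg threshold, and 5 mmHg, the plan's own stricter figure, is named as the non-inferiority margin.
- **Section 11.2, decision rule:** state that non-inferiority is concluded only if the one-sided 95% upper confidence limit of the mean within-child increase in ETCO₂ is below 5 mmHg. The one-sided level agrees with the test size in 11.1.
- **Section 11.2, condition:** say whether rest, mild exertion or both must meet the rule. Otherwise the mask could pass in one condition and fail in the other with no stated conclusion.
- **Section 11.2, interpretation:** state that a pass concerns the average rise only. Report beside it the already planned proportion above 50 mmHg sustained for at least 3 minutes, as the evidence on the upper bound of the 2.1 hypothesis. That proportion does not address the lower bound of 30.

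The cost is a few sentences of protocol wording and one decision about the deciding condition, with no new data, visits or children. The sponsor gives up the looser 10 mmHg reading.
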